6.13.5. Vital Signs and Other Physical Findings

Vital sign measurements and weight will be analyzed using continuous data (change from baseline) and categorical data (proportion of potentially clinically significant changes).

If there are multiple records of vital sign or weight measurements at baseline or a postbaseline visit, the last record will be used. Summary statistics will be presented for observed values at baseline and for change from baseline results at each scheduled postbaseline visit. Systolic and diastolic blood pressure and pulse (collected in sitting position), orthostatic diastolic and orthostatic systolic blood pressures and orthostatic pulse (measurement after 5 minutes in the supine position minus that after 2 and 5 minutes in the standing position), temperature, and weight by treatment group for all subjects in the safety population will be summarized.

With the large number of visits at which vital signs are scheduled to be measured, the MMRM model is not suitable for the change from baseline comparison of treatments. In the Placebo-Controlled period change from baseline to each post-baseline visit at which vital signs are taken will be assessed using an ANCOVA model with treatment and as independent factors and baseline value and age as covariates in the model. This analysis will be done separately for each vital sign parameter and weight. In the Delayed-Start period, these changes will be summarized.

The incidence of treatment-emergent abnormal high or low vital signs and weight will be presented by treatment group and visit. Treatment-emergent vital sign evaluations are defined for evaluations collected after the initiation of study medication. Abnormal criteria for postbaseline vital signs and weight are presented in Appendix 5. Any vital sign or weight meeting the criteria will be considered abnormal. In the Placebo-Controlled period, treatment differences in the proportion of subjects with treatment-emergent abnormal high or low vital signs and weight will be assessed between treatment groups using Fisher's Exact test at (1) any time and (2) by post-baseline visit.

For each vital sign at each post-baseline visit, only subjects who had a baseline result and had a nonmissing result at that post-baseline visit will be included in the denominator when computing the proportion of subjects with treatment-emergent high, low, or abnormal values.

Summary and analyses of change from baseline in weight will be provided. The proportion of subjects with a weight gain or loss of greater than or equal to 7 percent of baseline body weight

will be compared between treatment groups using Fisher's Exact test at each visit and at any time in the Placebo-Controlled period..

A listing of treatment-emergent abnormal vital signs and weight will also be presented by subject and visit across the Placebo-Controlled and Delayed-Start periods.

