- Skin examination must be supervised by a dermatologist. The baseline examination may be performed any time before randomization. Additional details are described in Section 9.4.8.

Table 2.2. Study Schedule, Protocol I8D-MC-AZET, Visit 2 through Visit 16 (Placebo-Controlled Period)

Visit No. a	V2 Randomization b	V3	V4	V5	V6	V7	V8	V9	V10	V11	V12	V13	V14	V15	V16	ED c
Study week		1	4	7	13	19	26	32 d ☎	39	45	52	58 d ☎	65	71	78	
Tolerance interval for Visit (days)		±3	±3	±7	±7	±7	±7	±7	±7	±7	±7	±7	±7	±7	±7	
Administrative																
Concomitant treatments	X	X	X	X	X	X	X	X	X	X	X	X	X	X	X	X
Inclusion/exclusion criteria review	X															
Dispense drug e	X	X	X	X	X	X	X		X	X	X		X	X	X	
Assess drug compliance f		X	X	X	X	X	X	X	X	X	X	X	X	X	X	X
Efficacy Measures (Study Partner)																
FAQ	X						X				X				X	X
ADCS-ADL	X						X				X				X	X
CDR g							X				X				X	X
NPI	X						X				X				X	X
EQ-5D	X					X				X					X	X
QoL-AD	X					X				X					X	X
RUD-Lite	X					X				X					X	X
Efficacy Measures (Patient)												•				
MMSE					X		X				X				X	X
ADAS-Cog 13	X				X		X		X		X		X		X	X
RBANS	X									X				X		X
QoL-AD	X					X				X					X	X
CDR g							X				X				X	X
Longitudinal Biomarker Measures																
Florbetapir amyloid PET (+/- perfusion)															$X^h$	$X^h$
OR h Lumbar puncture i														Xi		Xi

Visit No. a	V2 Randomization b	V3	V4	V5	V6	V7	V8	V9	V10	V11	V12	V13	V14	V15	V16	ED c
Study week		1	4	7	13	19	26	32 d ☎	39	45	52	58 d ☎	65	71	78	
Tolerance interval for Visit (days)		±3	±3	±7	±7	±7	±7	±7	±7	±7	±7	±7	±7	±7	±7	
MRI															X	X
Safety Measures																
12-Lead ECG j	X	X	X		X		X		X		X		X	X	X	X
Vital signs k	X	X	X	X	X	X	X		X	X	X		X	X	X	X
Body weight	X				X		X				X				X	X
C-SSRS  and Self-Harm Supplement Form	X	X	X	X	X	X	X		X	X	X		X	X	X	X
Adverse events	X	X	X	X	X	X	X	X	X	X	X	X	X	X	X	X
Laboratory Specimens																
Blood sample for plasma LY3314814 and AZ13569724 PK m			$X^{m}$	$X^{m}$		X m			X m	X m				$X^{m}$		X
Blood sample for plasma biomarkers	X		X				X				X			X		X
АроЕ	X															
Laboratory tests (see Appendix 2)	X		X	X	X		X		X		X		X		X	X
Pharmacogenetics	X															

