## 9.4.2. Vital Signs

For each patient, vital signs measurements, including temperature, should be conducted according to the Schedule of Activities (Section 2) at all office visits. Blood pressure and pulse will be measured supine and standing. Supine blood pressure and pulse rate should be taken after at least 5 minutes of supine rest. Standing blood pressure and pulse rate should be taken after 2 and 5 minutes in a standing position. Temperature will be recorded using an oral or tympanic thermometer.

Any clinically significant findings from vital signs measurement that result in a diagnosis and that occur after the patient receives the first dose of study treatment should be reported to the Sponsor or its designee as an AE via eCRF per Section 9.2.

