6.3. Handling of Dropouts or Missing Data

6.3.1. Handling Missing Data from Subject Dropouts

A likelihood-based mixed effects model for repeated measures will be used to handle missing data. The model parameters are simultaneously estimated using restricted likelihood estimation incorporating all of the observed data. Estimates have been shown to be unbiased when the missing data are missing at random and when there is ignorable non-random missing data.

Repeated measures analyses will only use data from visits where the data was scheduled to be collected (see Andersen and Millen 2013). When subjects discontinue from the study early, there may be efficacy or safety data measurements at visits where the variables were not scheduled to be collected. These data will be used in all other analyses.

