6.13.4. Clinical Laboratory Evaluations

Laboratory measures will be analyzed both as continuous data (change from baseline) and categorical or ordinal data (proportions of treatment-emergent abnormalities).

If there are multiple records of laboratory measurements at a baseline or post-baseline visit, the latest record will be used.

Summaries and analyses of continuous data (change from baseline) will use both conventional and International System of Units (SI units).

For the Placebo-controlled period, change from baseline to post-baseline visits will be compared between treatment groups using an MMRM model. For each lab analyte, the rank-transformation will be applied to the change from baseline for all subjects and all visits prior to analysis. Similarly, an independent rank transformation will be applied to the baseline values prior to analysis. The model for the fixed effects will include terms for: baseline, treatment, visit, and the treatment-by-visit interaction. This analysis will be done separately for each lab analyte. For the Delayed-Start period, mean change from baseline to post-baseline visits will be summarized.

For the Placebo-Controlled period, treatment differences in the proportions of subjects with treatment-emergent high or treatment emergent low or treatment-emergent abnormal laboratory values at (1) anytime and (2) each post-baseline visit will be assessed using Fisher's Exact Test. Treatment-emergent high or low abnormalities will be calculated using SI units. For each lab analyte, only those subjects who were low or normal at baseline and have at least one post-baseline measurement will be included in the denominator when calculating the proportion of subjects with treatment-emergent high values. Similarly, only subjects who were high or normal at baseline and have at least one post-baseline measurement will be included in the denominator when calculating the proportion of subjects with treatment-emergent low values. In addition, treatment differences in the proportion of subjects who were normal at baseline and change to abnormal high or abnormal low values at any post-baseline visit will be summarized. For the Delayed-Start period, the proportions will be summarized.

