6.13.6. Electrocardiograms

ECG measurements will be analyzed using continuous data (change from baseline) and categorical data (proportion of treatment-emergent abnormalities).

The analysis will be done for the following ECG measurements: heart rate, PR, QT, QTc, and RR intervals and QRS duration. All analyses of QTc will be carried out using the Fridericia correction (QTcF) method. These summaries will include data from each visit ECG measures are performed. In the Placebo-Controlled period, change from baseline to each post-baseline visit at which ECG measurements are taken will be assessed using an MMRM model. The model for the fixed effects will include terms for the following independent effects: baseline ECG score, treatment, visit, treatment-by-visit interaction, and age at baseline. This analysis will be done separately for each ECG parameter. These change from baseline will be summarized in the Delayed-Start period.

In the Placebo-Controlled period, incidence of treatment-emergent abnormal ECGs will be assessed by comparisons at (1) anytime and (2) each post-baseline visit between treatment groups with Fisher's Exact test. For analyses of treatment-emergent abnormal ECGs, baseline will be considered as all visits before the initiation of drug dose. For the Delayed-Start period, these incidences will be summarized.

Abnormal ECG criteria and criteria for abnormal QTcF prolongation are presented in Appendix 6. A second summary of QTc intervals will compare incidence of treatment-emergent increases at any time in four different groups: < 30msec, 30 <= and < 60 msec, > 60 msec, and > 75 msec. This second summary will correct the QT intervals using Fridericia correction (QTcF) and using a large clinical trial population based correction factor (QTcLCTPB).

Treatment-emergent high ECG parameters (heart rate, PR interval, QRS duration, QT and QTcF intervals) are the values which are low or normal at all baseline visits and fall into the high abnormal categories post-baseline. Similarly, treatment-emergent low ECG parameters (Heart Rate, PR interval, QRS duration) are the values which are high or normal at all baseline visits and fall into the low abnormal categories above.

In the Placebo-Controlled period, treatment differences in the proportion of subjects who have normal baselines with a change to abnormal high or abnormal low values at any post-baseline visits will be summarized. In the Delayed-Start period, these proportions will be summarized.

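### SAP 6.13.5 sets MMRM aside because of the number of visits, but body weight has only four post-baseline visits, so its Week 78 comparison gives up precision for a reason that does not apply to it

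*SAP*

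**What the plan says.** SAP 6.13.5 gives its reason for avoiding a repeated-measures model: "With the large number of visits at which vital signs are scheduled to be measured, the MMRM model is not suitable". In its place, "change from baseline to each post-baseline visit at which vital signs are taken will be assessed using an ANCOVA model", with baseline value and age as covariates. Weight is included: "This analysis will be done separately for each vital sign parameter and weight".

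Elsewhere the SAP relies on repeated-measures models. Section 6.3.1, on dropouts, says "A likelihood-based mixed effects model for repeated measures will be used to handle missing data". For ECG (6.13.6), "change from baseline to each post-baseline visit at which ECG measurements are taken will be assessed using an MMRM model". For laboratory analytes (6.13.4), "change from baseline to post-baseline visits will be compared between treatment groups using an MMRM model". The primary ADAS-Cog13 analysis (6.12.1.1) is an MMRM with unstructured covariance.

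On the schedule, protocol 9.4.2 says "vital signs measurements, including temperature, should be conducted according to the Schedule of Activities (Section 2) at all office visits". Weight has its own, much sparser row in protocol Table 2.2: "Body weight X X X X X X". The first of those six marks is Visit 2 (baseline) and the last is the early-discontinuation visit. The four between are Visits 6, 8, 12 and 16.

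**The concern.** The reason given concerns how often vital signs are measured. Weight is measured far less often, and less often than three other sets of endpoints to which the same SAP applies MMRM. Weight seems to have been carried along with the vital signs without a reason of its own.

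The choice matters because SAP 6.13.5 names no imputation for this ANCOVA. SAP 6.1.1 describes last observation carried forward only for analyses that use it, and 6.13.5 does not invoke it. The natural reading is that each fit uses the patients with a weight at that visit. That is an inference, since the SAP does not label the analysis observed-case. On that reading, the Week 78 comparison borrows nothing from the earlier weights of patients who withdrew or whom the June 2018 stop reached before Week 78. At stake are the precision of a safety estimate and, under some withdrawal patterns, its bias.

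**Working it through.** **Visit counts.** Scheduled post-baseline visits in protocol Table 2.2, with k(k+1)/2 parameters for an unstructured covariance over k visits:

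| Measure | Weeks | k | Parameters | SAP model |
|---|---|---|---|---|
| Weight | 13, 26, 52, 78 | 4 | 10 | ANCOVA by visit |
| ADAS-Cog13 | 13, 26, 39, 52, 65, 78 | 6 | 21 | MMRM |
| Laboratory | 4, 7, 13, 26, 39, 52, 65, 78 | 8 | 36 | MMRM on ranks |
| ECG | 1, 4, 13, 26, 39, 52, 65, 71, 78 | 9 | 45 | MMRM |
| Vital signs | 1, 4, 7, 13, 19, 26, 39, 45, 52, 65, 71, 78 | 12 | 78 | ANCOVA by visit |

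Weight has the fewest visits of the five.

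**Patients absent at Week 78.** Protocol 5.2 assumes 25% discontinuation among 1899 randomized. 1899 × 0.75 = 1424, which reproduces its completer figure. 1899 − 1424 = 475 patients would have no Week 78 weight. The early stop adds to this by a number that the documents do not give.

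**Precision.** Let m be the share without a Week 78 weight and ρ the correlation between the last observed change and the Week 78 change. With n patients and variance σ² per arm:

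- ANCOVA at Week 78: σ² / [n(1 − m)]
- Likelihood model: (σ²/n) × [ρ² + (1 − ρ²)/(1 − m)]
- Ratio, ANCOVA to likelihood: 1 / (1 − mρ²)

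The documents give no ρ for weight, so 0.6 to 0.9 is an assumption.

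| m | ρ = 0.6 | ρ = 0.7 | ρ = 0.8 | ρ = 0.9 |
|---|---|---|---|---|
| 0.25 (planned dropout) | 1.10 | 1.14 | 1.19 | 1.25 |
| 0.50 (assumed, with the stop) | 1.22 | 1.32 | 1.47 | 1.68 |

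Taking square roots, the ANCOVA confidence interval is about 5% to 12% wider at m = 0.25 and 10% to 30% wider at m = 0.50. The formula credits every patient who misses Week 78 with an earlier weight. Patients who left before Week 13 have none, so the real gain is somewhat smaller.

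**Bias.** This was checked by simulation with assumed inputs: 633 per arm, individual 78-week slopes with SD 4 kg, visit noise with SD 1.5 kg, and a true Week 78 difference of −1.0 kg. Under completely random dropout, both methods return −1.0. In a second scenario, the same withdrawal rule applied in both arms, with the log-odds rising by 0.25 per kg lost at the previous visit. About 22% of placebo and 24% of drug patients then missed Week 78. A run of 1,000 trials gave −0.93 for observed-case and −0.98 for the likelihood estimate. Repeating it with 10,000 trials to reduce simulation noise gave −0.96 and −1.00. The observed-case shortfall is therefore about 4%. It arises because more drug patients lose weight and so more of them leave.

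**The case against.** Several points on the other side stand.

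- A reader might infer that the weights of patients who left early are discarded. They are not: the ANCOVA is run at every visit, so the Week 13, 26 and 52 weights are compared at those weeks. They are only not used to inform Week 78.
- ANCOVA for a safety variable is within the SAP's framework. Section 6.2 provides for it, and the missing-at-random statement in 6.3.1 describes likelihood models rather than binding every safety endpoint.
- Withdrawn patients are not lost to the safety review. The comparisons of 7% weight change and of abnormal values at any time count a patient whose event was recorded before withdrawal.
- MMRM has a cost of its own. Under 6.3.1 it would exclude weights taken at a discontinuation visit where weight was not scheduled. The Week 78 ANCOVA does not use those weights either, so this calls for a mapping rule and does not defeat the change.

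A stronger reading is that the ANCOVA conceals harm on drug. Scenarios can be built in which it understates a 1 kg difference by 13% to 49%, against 0% to 1% for MMRM. They require weight-driven withdrawal in the drug arm alone, and nothing in the documents points to that. MMRM does well there partly by construction, because withdrawal was made to depend on recorded weights. Loss between weight visits, which are up to 26 weeks apart, would bias both methods.

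A reader might also extend the argument to blood pressure, pulse and temperature. Those do have 12 visits, with sparse late data after the stop, and preferring a simpler model there is defensible.

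**Conclusion.** The point holds for body weight. The stated reason does not describe weight's schedule, and the SAP's use of MMRM at 6, 8 and 9 visits shows that four is no obstacle.

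The consequence is mainly lost precision at Week 78: a variance ratio of about 1.1 to 1.25 at the planned 25% missing, and 1.2 to 1.7 if half are missing. These figures rest on the assumed correlation of 0.6 to 0.9, on an unstated missing share after the stop, and on reading the ANCOVA as observed-case. Administrative stopping alone costs precision rather than causing bias. Bias in the difference needs weight-related withdrawal that differs between arms, in strength or in frequency. The documents neither show nor exclude that.

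Severity is minor. SAP 6.1 says no test will be read as statistically significant, and 6.1.1 treats all Placebo-Controlled results as hypothesis-generating. The choice affects a reported safety estimate and its interval, not a confirmatory conclusion.

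**What to change.** In SAP 6.13.5, separate weight from the vital signs.

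- Analyse change in weight over the Placebo-Controlled period with the MMRM form of 6.13.6: baseline weight, treatment, visit, treatment-by-visit and age at baseline. Specify an unstructured covariance, since 6.13.6 names none. Report each dose against placebo at Weeks 13, 26, 52 and 78.
- State how weights from early-discontinuation and futility visits are assigned to scheduled weight visits, for example by a window fixed in the SAP, and what happens to those outside it.
- Keep the visit-wise ANCOVA for weight as supportive.
- Limit the sentence on the number of visits to blood pressure, pulse and temperature, whose analysis may stay as planned.
- Leave the 7% weight-change and potentially clinically significant tables unchanged.

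The cost is SAP wording and a little programming, mostly reuse of the ECG model, with no new data. The one real downside is that off-schedule discontinuation weights stay out of the MMRM under 6.3.1 unless the mapping rule brings them in.

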### 9.4.9.1. Adverse Events of Special Interest

Adverse events of special interest will include:

- Adverse eye effects including retina (Section 9.4.7)
- Adverse skin effects including rash (Section 9.4.9.3) and hypopigmentation (Section 9.4.8)
- Peripheral nervous system, central nervous system and muscle effects
- Liver toxicity (Section 9.4.9 and Section 8.1.1)
- Cardiovascular (CV)-type events (including, but not limited to, orthostatic hypotension and QT prolongation) (Section 9.4.9.2)

The topics listed above, as well as new topics which may be subsequently determined by the Sponsor, will be subject to enhanced surveillance activities. Additionally, the topics above will be analyzed for presentation in the Clinical Study Report in accordance with the Statistical Analysis Plan (SAP).

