Appendix 4. Potentially Clinically Significant Vital Signs and Weight

Vital Sign Parameter (Unit)	Postbaseline Low Criteria	Postbaseline High Criteria	
Sitting Systolic Blood Pressure	Absolute value ≤90 and ≥20 decrease	Absolute value ≥160 and ≥20 increase	
(mmHg)	from baseline	from baseline	
Sitting Diastolic Blood Pressure	Absolute value ≤50 and ≥10 decrease	Absolute value ≥100 and ≥10 increase	
(mmHg)	from baseline	from baseline	
Sitting Pulse (bpm)	Absolute value <50 and ≥15 decrease	Absolute value >100 and ≥15 increase	
	from baseline	from baseline	
Weight	≥7% decrease	≥7% increase	
Vital Sign Parameter (Unit)	Postbaseline Criteria for Abnormality		
Orthostatic Systolic Blood	≥20 decrease in systolic blood pressure (supine to standing)		
Pressure (mmHg)	(ie, supine minus standing ≥20)		
Orthostatic Diastolic Blood	≥10 decrease in diastolic blood pressure (supine to standing)		
Pressure (mmHg)	(ie, supine minus standing ≥10)		
Orthostatic Pulse (bpm)	\leq -30 decrease (supine to standing) (ie, supine minus standing \leq -30)		
Temperature	Absolute value ≥38.3°C and ≥1.1°C increase from baseline		
	(Absolute value ≥101°F and ≥2°F increase from baseline)		

Abbreviations: bpm=beats per minute, NA=not applicable.

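### The three orthostatic criteria count patients who already met them before dosing as treatment-emergent, which overstates incidence in every arm and usually pulls the risk ratio toward 1

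*SAP*

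**What the plan says.** SAP 6.13.5 sets three rules for the categorical analysis of vital signs.

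- Timing: "Treatment-emergent vital sign evaluations are defined for evaluations collected after the initiation of study medication".
- Abnormality: "Any vital sign or weight meeting the criteria will be considered abnormal".
- By-visit denominator: "only subjects who had a baseline result and had a nonmissing result at that post-baseline visit will be included in the denominator".

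None of these asks whether the patient was free of the abnormality at baseline. Arms are compared by Fisher's exact test, at any time and by visit, in the Placebo-Controlled period.

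The criteria are in SAP Appendix 4. Sitting systolic pressure, sitting diastolic pressure and sitting pulse each pair an absolute limit with a change from baseline. Temperature does the same: "Absolute value ≥38.3°C and ≥1.1°C increase from baseline". Weight is itself a percentage change. The orthostatic rows are differences between two positions within one visit: "≥20 decrease in systolic blood pressure (supine to standing", "≥10 decrease in diastolic blood pressure (supine to standing", and a supine-minus-standing pulse difference of -30 bpm or lower.

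Elsewhere the SAP conditions on baseline. A treatment-emergent high ECG value must be "low or normal at all baseline visits and fall into the high abnormal categories post-baseline". Section 6.13.4 removes patients already high from the denominator for treatment-emergent high laboratory values, and likewise for low values. Section 6.13.2 requires adverse events to be new or worse after randomization.

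Protocol 9.4.9.1 lists cardiovascular-type events as being of special interest, "including, but not limited to, orthostatic hypotension and QT prolongation".

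**The concern.** A patient with a 25 mmHg systolic drop at Visits 1 and 2 and the same drop at Week 1 is reported as treatment-emergent. Nothing emerged on treatment. The sitting, weight and temperature rows guard against this through their change conditions. The orthostatic rows have no guard.

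The population makes this more than theoretical. Patients are 55 to 85 years old. Exclusion [17] removes syncope due to orthostatic hypotension but not a symptom-free postural drop. Vital signs are scheduled at 12 post-baseline visits in the Placebo-Controlled period, so a patient prone to such drops has many chances to be flagged in the any-time table.

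At stake is how the table reads: the rate attributed to treatment in each arm, and the drug-to-placebo ratio for a finding that the protocol singles out.

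**Working it through.** **Plan figure used.** The documents give no rate or power for the orthostatic rows. The only arm size is 633 (Protocol 10.1, SAP 5.2). It reproduces: 554 / (1 - 0.25 × 0.50) = 633.1. An independent calculation of the completers needed gives 555 per arm against the stated 554.

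**Notation.** b = share meeting the criterion at baseline. p0, p1 = new-onset rates in baseline-negative patients on placebo and drug. q0, q1 = probability that a baseline-positive patient meets it again at any post-baseline visit. Values for all five are assumptions.

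**As-written proportion** in an arm = (1 - b) × p + b × q.

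**Equal recurrence.** p0 = 0.15, p1 = 0.20 (ratio 1.33), q0 = q1 = 0.80. For b = 20%:

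- placebo 0.8 × 0.15 + 0.2 × 0.80 = 0.280
- drug 0.8 × 0.20 + 0.2 × 0.80 = 0.320
- share of placebo cases present before dosing 0.160 / 0.280 = 57%

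| b | Placebo v drug, as written | Risk difference | Risk ratio | Placebo cases present before dosing | z as written (n = 633) | z restricted (n = 633 × (1 - b)) |
|---|---|---|---|---|---|---|
| 10% | 21.5% v 26.0% | 4.5 points | 1.21 | 37% | 1.88 | 2.22 |
| 20% | 28.0% v 32.0% | 4.0 points | 1.14 | 57% | 1.55 | 2.09 |
| 30% | 34.5% v 38.0% | 3.5 points | 1.10 | 70% | 1.30 | 1.96 |

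The restricted analysis keeps a risk difference of 5.0 points and a ratio of 1.33.

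A second set of assumed rates (new onset 20% v 27%, recurrence 0.80 in both arms, b = 20%) gives 32.0% v 37.6%. The ratio falls from 1.35 to 1.18, and power at two-sided 0.05 from 75% to 55%.

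**Unequal recurrence.** Keep q0 = 0.80 and the 15% v 20% onset rates, but set q1 = 0.90:

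| b | Placebo v drug, as written | Risk difference | Risk ratio | z as written | z restricted |
|---|---|---|---|---|---|
| 10% | 21.5% v 27.0% | 5.5 points | 1.26 | 2.28 | 2.22 |
| 20% | 28.0% v 34.0% | 6.0 points | 1.21 | 2.31 | 2.09 |
| 30% | 34.5% v 41.0% | 6.5 points | 1.19 | 2.39 | 1.96 |

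The risk difference and z now exceed the restricted values, while the ratio stays below 1.33.

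**When each measure is diluted.**

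- Risk difference = (1 - b)(p1 - p0) + b(q1 - q0). It falls only if q1 - q0 is smaller than p1 - p0.
- The as-written ratio is a weighted average of p1/p0 and q1/q0. The weight on q1/q0 is the share of placebo cases present before dosing. The ratio falls below p1/p0 whenever q1/q0 is smaller than p1/p0. With q0 = 0.80, q1/q0 cannot exceed 1 / 0.80 = 1.25, so a new-onset ratio of 1.33 must be diluted.

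**Type I error.** With no drug effect (20% onset in both arms, b = 20%, recurrence 0.80), simulated Fisher tests rejected in 3.9% of runs as written and 4.4% restricted. Randomization balances the baseline-positive patients.

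**The case against.** A reader might infer that the rule necessarily hides a real drug effect. The documents do not support that. Randomization balances baseline status, not what happens after dosing, and a drug that causes postural drops may act on patients already prone to them. The second table shows that the as-written comparison can then be the more sensitive one. This stands, and it limits the claim about risk difference and power. The overstated incidence remains, and so does the ratio dilution in the scenarios shown.

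A reader might also infer that all such patients enter the trial. Exclusion [29] lets an investigator exclude a clinically important vital sign abnormality at screening, and supine and standing pressures are taken at that visit. It is discretionary and sets no orthostatic threshold, so it may lower prevalence by an unknown amount.

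Nor is the event of special interest left without a baseline-aware analysis. The blood-pressure cluster in SAP 6.13.3 uses adverse events that are new or worse after randomization. Section 6.13.5 also compares change from baseline by ANCOVA with baseline as a covariate. Both are unaffected. They complement the table but do not replace it: one depends on events being reported, the other compares means.

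Protocol 10.3.4 asks only for a baseline and a post-baseline observation, and 6.13.5 complies. That is a minimum. The SAP adds stricter rules for laboratory values and ECGs under the same sentence. Finally, SAP 6.1 makes p-values descriptive after the futility stop, so the z statistics carry little weight. The displayed rates and ratios are what readers will use.

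**Conclusion.** The point holds as a mislabelling of pre-existing cases in three rows of a safety table. As written, treatment-emergent orthostatic incidence is overstated in every arm. The risk ratio is pulled toward 1 unless the drug raises recurrence among baseline-positive patients proportionally at least as much as it raises new onset.

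The size cannot be fixed from the documents. Under the assumed onset rates of 15% v 20% and 80% recurrence in both arms, baseline prevalence of 10% to 30% takes the ratio from 1.33 to between 1.21 and 1.10. Loss of risk difference and power is conditional on recurrence being similar across arms. The false-positive rate is not inflated, and no conclusion about the drug's orthostatic safety follows from this point alone. Orthostatic pulse is affected by the same rule but is not itself named as being of special interest.

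**What to change.** In SAP 6.13.5, for the three orthostatic rows in the Placebo-Controlled period, define treatment-emergent as meeting the Appendix 4 criterion after first dose in a patient who did not meet it at any pre-dose visit (Visits 1 and 2, matching the ECG rule). Limit numerator and denominator to those patients. State how the 2-minute and 5-minute standing readings combine into one result per visit.

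Add a shift table of baseline against worst post-baseline status, or a separate row for baseline-positive patients, so that no event is hidden and recurrence on drug stays visible. In the Delayed-Start summaries, apply the corresponding baseline from SAP 6.1.2. In the same edit, correct the cross-reference: 6.13.5 points to Appendix 5 for the vital sign criteria, which are in Appendix 4.

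The cost is SAP wording, one programming filter and one small table, with no new data. The downside is a somewhat smaller denominator for three rows.
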